## Scientific Background

### SIGNIFICANCE

A1. Mental health diagnoses are common and impairing among youth transitioning to college. Recent research indicates that 33% of college freshmen screen positive for at least one mood, anxiety, or substance disorder. Unfortunately, these and other common psychiatric disorders (e.g., Attention Deficit Hyperactivity Disorder ADHD, eating disorders) can profoundly affect successful college transition. College students rank mental health concerns among the top four factors that interfere with their academic performance, and most students who leave college without graduating do so due to mental health reasons.

A2. Engagement in mental healthcare among college students. Despite the prevalence and impairment associated with mental health conditions among college students, treatment rates are low. Research demonstrates that 60% of college students with a mental health problem report the same problem two years later, and within this group (i.e., those whose condition persisted over 2 years), less than half received treatment during that same period of time. Young adults are also more likely to self-discontinue antidepressants than older adults. These data are particularly concerning given that earlier onset of psychiatric disorders is associated with poorer outcomes and greater symptom severity.

A2. The import of mental health self-efficacy among transition age youth. Although many of these youth may have received a range of services in pediatric care (e.g., medication management, psychiatry, therapy) and within the school system (e.g., individualized education plans) prior to college transition, such services often rely on the involvement of parents or guardians in supporting youth, for example, to schedule and attend appointments or refill and administer medications. Once these youth transition to college, they are often on their own, responsible for navigating new systems of care, and must assume responsibility for scheduling appointments, filling medications, and seeking out additional services (e.g., academic accommodations). Furthermore, many college students with pre-existing mental health disorders do not disclose their conditions to their school and/or seek services for other reasons, including lack of awareness of resources, concerns about stigma, and desire for a “fresh start.”

Thus, while many students transitioning to college may benefit from linkage with mental health supports on campus, not all have the knowledge, skills and beliefs to manage their mental healthcare independently, a concept referred to as “mental health self-efficacy.” Not surprisingly, studies show mental health self-efficacy is associated with mental health outcomes and functioning among young adults. Low mental health self-efficacy, together with mental health symptoms, and further exacerbated by common stressors associated with initiating higher education (e.g, academic and social pressures, decreased structure) can culminate in dire consequences for college students including hospitalization, academic probation/failure, and even suicide, rendering mental health self-efficacy an important treatment target for transition-age students.

A3. Interventions to increase mental health self-efficacy. Consistent with cognitive models of help-seeking, interventions to date designed to enhance engagement with mental health services largely

focus on increasing mental health literacy and decreasing stigma. A recent meta-analysis on studies using these approaches found modest improvements in help-seeking cognitions; 1 trial showed small improvements in linkage to mental health care; only 1 targeted adolescents, and most were delivered in-person. Thus, innovative approaches are needed that specifically target mental health self-efficacy among college students to enhance outcomes for this high-risk population.

A4. New Approaches: The Role for Mobile Technology. The ubiquity of mobile communication technology (i.e., cellphones) across age and socio-economic status makes it an ideal platform to reach at-risk individuals. By interacting with individuals in their daily lives over time, mobile digital interventions could be particularly useful to modify cognitive and motivational components of mental health self-efficacy. Text messaging (TM) is a form of digital communication that is especially useful at modifying adolescent health behaviors, including studies by our group on alcohol and risky sexual behavior (see Preliminary Data). Recent evidence also suggests that TM interventions can improve mental healthcare outcomes youth engaged in treatment, yet promise for promoting mental health self-efficacy remains unknown. We will thus develop a TM intervention targeting mental health self-efficacy for youth transitioning to college.

#### INNOVATION

Our TM intervention, “Text to Connect” (T2C), is the first mobile digital intervention to target mental health self-efficacy among transition-age youth with mental health conditions. Because adolescents rely heavily on TM for communication, T2C may be particularly developmentally appropriate. T2C pathways are tailored based on the youth’s needs, thus making material individualized and personal.

#### PRELIMINARY DATA

Text to Connect (T2C) Version 1 for Adolescents. In the context of a Center-funded treatment development phase, the current study team successfully developed and tested a preliminary version of T2C designed to enhance follow-through with mental health treatment for youth (age 12-18) referred for co-located treatment in primary care. The T2C system was successfully built in collaboration with OAC and implemented with 24 youth to date recruited across 4 CCP practices and STAR. From this pilot trial, we determined that the TM intervention itself was highly promising, but also identified an unmet need among transition-age youth for the technology developed, with some modifications. As such, this pilot work demonstrates the team’s success building TM interventions for youth, the resulting intervention serves as a foundation for the T2C system proposed herein, and helped the team identify a significant clinical need and treatment target for this system.

Interactive Text Messaging Interventions Effect Youths’ Health Behavior. Co-I [name] is an expert in the development, implementation and testing of TM interventions to modify health-related behavior in young people. His work demonstrated that for young adults presenting to the emergency department who screen positive for hazardous alcohol use, the TM intervention he developed was associated with greater reductions in binge drinking days (IRR=.69; 95% CI=.59-.79) and lower binge drinking prevalence (OR=.52; 95% CI=.26-.98) compared with controls. He has also applied TM interventions to other youth health behaviors in the emergency department, including sexual risk behaviors and antibiotic adherence.

A Brief Motivational Intervention Improves Medication Adherence for Adolescents with Bipolar Disorder. In a recently completed R34 (MH92424), PI [name] developed and examined an in-person Brief Motivational Intervention (bMI) targeting medication adherence for adolescents with bipolar disorder. A randomized trial demonstrated significant improvement in objective medication adherence among adolescents who received the bMI, vs treatment as usual; the bMI was most potent for adolescents with lower baseline adherence and higher treatment expectancy. Together, these studies demonstrate the team's success examining disseminable motivational interventions and TM platforms for youth health behavior change.

## Study Objectives

This protocol represents the 2nd phase of the ETUDES Center protocol (also known as Study 2 of 3) for Text2Connect Phase 1b. Please reference STUDY18120039 for additional ETUDES Center background leading to the development of this protocol, including the planning toward making adjustments to the initially tested intervention tailored to the real-world settings in which they are implemented.

Over 1/3 of first-year college students screen positive for at least one mood, anxiety, or substance disorder. Unfortunately, despite the prevalence and impairment associated with mental health conditions among college students, treatment rates are low. Research demonstrates that 60% of college students with a mental health problem report the same problem two years later, and less than half received treatment during that time.

This transition period to college presents innumerable challenges that render treatment engagement low for young adults with mental health conditions starting college. Although these youth may have received a range of services in pediatric care (e.g., medication management, psychiatry, therapy) and within the school system (e.g., individualized education plans), such services often rely on the involvement of parents or guardians in supporting youth, for example, to schedule and attend appointments or refill and administer medications. Once these youth transition to college, they are often on their own, responsible for navigating new systems of care, and must assume responsibility for scheduling appointments, filling medications, and seeking out additional services (e.g., accommodations).

As such, not all young adults with mental health conditions have the knowledge, skills and beliefs to manage their own mental health and care independently, a concept referred to as "mental health self-efficacy." Not surprisingly, studies show mental health self-efficacy is associated with mental health outcomes and functioning among young adults. Low mental health self-efficacy, together with mental health symptoms, and further exacerbated by common stressors associated with initiating higher education (e.g. academic and social pressures, decreased structure) can culminate in dire consequences for college students including hospitalization, academic probation/failure, and even suicide.

Digital interventions using mobile communication such as text messaging (TM) could be useful to enhance mental health self-efficacy among young adults during the transition to college. Potential benefits of TM approaches include the ability to prompt awareness of treatment targets in daily life and

deliver tailored knowledge and skills to enhance self-efficacy, thereby improving outcomes. Recent studies suggest TM interventions may improve retention in mental health care for depressed adolescents already in treatment. Yet, effective approaches to enhancing mental health self-efficacy for transition-age youth remains unknown.

To enhance outcomes for transition-age youth with mental health disorders during the vulnerable period that occurs during their first several months of college, we propose an automated TM intervention, "Text to Connect" (T2C), that aims to increase mental health self-efficacy through psychoeducation, self-monitoring of symptoms and stressors, and cues to action for college-bound youth. We propose a pilot randomized controlled trial for 50 youth with a current psychiatric diagnosis who are transitioning to college. Youth will be identified by their treatment providers at 1 of 3 clinics (pediatric primary care clinic, CCP Waterdam; Services for Teens at Risk, STAR Clinic; and Child and Adolescent Bipolar Spectrum Clinic, CABS, Western Psychiatric Hospital) within 6 weeks of starting a higher education program. Consenting participants will be randomized on a 2:1 randomization scheme to either receive T2C (n=30) or a link to brief psychoeducational videos about mental health (PE; n=20). All participants will then complete a brief battery of self-report assessments online at baseline and again monthly through month 4. Youth randomized to receive PE will receive a text message with the link to the webpage with the psychoeducational videos. Youth randomized to receive T2C will be onboarded and initiate the TM intervention that sends automated prompts at minimum monthly through month 4.

Aim 1. To examine the feasibility of T2C for transition-age youth with psychiatric disorders (n=3 clinics, 50 adolescents). Youth randomized to receive T2C will:

Hypothesis 1a. engage with T2C at high rates (>70% response rate to SMS prompts).

Hypothesis 1b. report high levels of satisfaction (>70% satisfaction) and usability with T2C.

Aim 2. To examine the impact of T2C versus PE on mental health self-efficacy, symptoms and functioning, and treatment engagement. Over 4 months, youth who receive T2C, as compared with youth who receive PE, will report:

Hypothesis 2a (Primary). Greater mental health self-efficacy

Hypothesis 2b (Secondary). Lower symptom severity and greater psychosocial functioning

Hypothesis 2c (Secondary). Higher rates of follow-through with mental health services

Our team is ideally suited to conduct the proposed study. PI [name] has extensive experience developing and testing psychosocial interventions for adolescents, including motivational interventions for mood-disordered adolescents and mHealth, and Co-I [name] is expert in developing and testing TM interventions to modify health-related behavior in young people. [name] is a pediatrician and community champion devoted to enhancing mental health outcomes for adolescents and young adults.

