## Study Design & Method

This study is a randomized trial with a 2:1 allocation in favor of the intervention vs. treatment as usual (TAU).

T2C Onboarding. The participant will be prompted to text a unique keyword to initiate T2C. Upon study entry, participants will receive a series of welcome messages describing what to expect over the intervention period, expectations for response, and ways to reduce breach of privacy. For example: "Welcome to T2C. Over the next 4 months we'll be checking in by text message. Set up a password on your phone and erase messages you do not want anyone to see after reading them." We will indicate they can drop out of the T2C program at any time by texting "Quit." [name] has successfully used this onboarding process prior studies. Study staff will assist youth with any technical difficulties.

T2C Intervention. T2C aims to increase mental health self-efficacy through psychoeducation, self-monitoring of symptoms and stressors, and cues to action for college-bound youth. Specifically, each monthly check-in starts with a text prompt inquiring about general well-being. Based on the participant's response, the participants then receive either general psychoeducational videos and prompts to continue to monitor mental health (in the event of wellness) or are then prompted to endorse stressors and symptoms they are experiencing to prompt awareness of treatment targets in daily life. A text prompt then assesses the participant's self-reported confidence in ability to manage stressors and symptoms. Tailored knowledge and skills are then texted to the participant to enhance self-efficacy. Participants who endorse stressors/symptoms can opt to receive follow-up texts one week later to re-assess. Participants who endorse low confidence in ability to manage stressors and symptoms are prompted to seek treatment and provided resources.

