## Statistical Considerations

Aim 1. To examine the feasibility of T2C for transition-age youth with psychiatric disorders (n=3 clinics, 50 adolescents). Youth randomized to receive T2C will:

Hypothesis 1a. engage with T2C at high rates (>70% response rate to SMS prompts). We will calculate TM response rates within and between individuals. Per our proposed design, each adolescent will contribute up to 12 responses per timepoint.

Hypothesis 1b. report high levels of satisfaction (>70% satisfaction) and usability (PSSUQ>6) with T2C. We will compute mean satisfaction (CSQ) and usability (PSSUQ) at 4 month follow-up.

Aim 2. To examine the impact of T2C versus PE on mental health self-efficacy, symptoms and functioning, and treatment engagement. Over 4 months, youth who receive T2C, as compared with youth who receive PE, will demonstrate:

Hypothesis 2a (Primary). Greater mental health self-efficacy (MHSES, SE-SMHC).

Hypothesis 2b (Secondary). Lower symptom severity (CCAPS) and greater psychosocial functioning (CAQ).

Hypothesis 2c (Secondary). Higher rates of follow-through with mental health services (C-SRI).

For each of the proposed outcomes (a-c), we will construct mixed-effect models to examine for between-group differences in each outcome. Mixed-effects models are recommended for analysis of repeated-measures data and can properly account for missing data as well as multivariate outcomes.

Power Analysis. The proposed study is a preliminary randomized pilot study. We expect that the small sample will provide sufficient comparison data to guide the design of a larger-scale controlled study that would be sufficiently powered to determine the efficacy of the intervention.

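### The self-report baseline is placed after randomization with no rule withholding allocation until it is submitted, so Aim 2 estimates that use baseline may be biased

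*Combined protocol and SAP*

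**What the plan says.** Study Objectives sets out the sequence. First, "Consenting participants will be randomized on a 2:1 randomization scheme". The next sentence reads: "All participants will then complete a brief battery of self-report assessments online at baseline and again monthly through month 4". Delivery is described after that: "Youth randomized to receive PE will receive a text message with the link to the webpage with the psychoeducational videos", and "Youth randomized to receive T2C will be onboarded and initiate the TM intervention that sends automated prompts at minimum monthly through month 4".

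Study Design & Method, under T2C Onboarding, has the participant text a keyword to start and adds: "Upon study entry, participants will receive a series of welcome messages describing what to expect over the intervention period". Study entry is not defined relative to the baseline survey.

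For Aim 2, Statistical Considerations says "we will construct mixed-effect models to examine for between-group differences in each outcome". It does not say whether baseline is a repeated response, a covariate or unused. The same section expects the pilot to give "sufficient comparison data to guide the design of a larger-scale controlled study".

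The text available contains no statement on participant blinding, on when the arm is disclosed, or on baseline being submitted first. Part of the document was removed before review and could not be checked.

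**The concern.** A baseline measurement protects a comparison only if allocation cannot have influenced it. Here the stated order is consent, randomization, baseline. The online battery is the only assessment described for Aim 2, so it supplies the primary self-efficacy score. The outcome is subjective, and the arms differ visibly: four months of interactive texting against a link to short videos. A participant who knows that support is coming, or who has already had the T2C welcome messages, might rate their own confidence differently. The documents do not show that this happens; they leave it possible.

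If it did happen, a change-score, group-by-time or baseline-adjusted effect would absorb the baseline shift. A raised T2C self-efficacy baseline would bias against T2C, and a lowered one in its favor. Baseline completion could also come to differ by arm. A baseline cannot be collected again later, and the resulting estimates are meant to inform a larger trial.

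**Working it through.** **No plan figure to reproduce.** The documents give no alpha, effect size, SD, correlation or power for Aim 2.

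**Inputs.** From the documents: 30 T2C and 20 PE participants; surveys at baseline and months 1 to 4. Assumed: unit SD; equal correlation r between any two surveys; a shift d in the T2C arm's mean at baseline only; no true effect; two-sided 5% test.

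**Bias in the T2C minus PE contrast**
- Month-4 change score: −d
- Month-4 score adjusted for baseline: −r × d
- Month-4 score alone: 0
- Linear group-by-time over five surveys: centered times are −2, −1, 0, 1, 2 with sum of squares 10, so the slope shifts by −(2/10) × d per month. Over 4 months this is −0.8 × d.
- Group difference averaged over all five surveys: +d/5

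**Standard errors.** A mean difference has SE √(1/30 + 1/20) = 0.289 SD. At r = 0.6:
- Change score: 0.289 × √(2 × 0.4) = 0.258
- Baseline-adjusted: 0.289 × √(1 − 0.36) = 0.231

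**Results at d = 0.2, r = 0.6** (rejection rates from 20,000 simulated trials)

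| Analysis | Bias (SD) | Rejection under no effect |
|---|---|---|
| Change score, month 4 | −0.20 | 11.9% |
| Baseline-adjusted, month 4 | −0.12 | 8.1% |
| Linear group-by-time, over 4 months | −0.16 | 10.5% |
| Mean of all five surveys | +0.04 | 5.3% |
| Month 4 alone | 0.00 | 4.9% |

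At d = 0, rejection is 4.8% to 5.0%. A separate simulation of 4,000 trials per setting, with r from 0.3 to 0.7, agreed with the first three formulas. At d = 0.2 and r = 0.5 it gave −0.203, −0.101 and 0.000. With d = −0.2 the signs reverse.

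**Range for d from 0.1 to 0.3 and r from 0.4 to 0.8**
- Change score: bias 0.10 to 0.30 SD, rejection 6.3% to 36.4%.
- Baseline-adjusted: bias 0.4 × 0.1 = 0.04 to 0.8 × 0.3 = 0.24 SD, rejection 5.3% to 26.4%.

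**Allocation.** 30/20 is 1.5:1, not the stated 2:1, which is a separate matter. With 33/17, d = 0.2 and r = 0.6, rejection is 11.1% (change score) and 7.7% (adjusted), so this result barely depends on it.

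**Cost of ignoring baseline instead.** The SE of month 4 alone, relative to the adjusted contrast, is 1/√(1 − r²): 1.09, 1.25 and 1.67 at r = 0.4, 0.6 and 0.8. At 0.6, equal precision would take 50/(1 − 0.36) = 78 participants instead of 50.

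**The case against.** The strongest reply is that this is loose drafting. The sequence sits in a summary paragraph, the word *then* may simply introduce the survey schedule, and delivery of both interventions is described after the baseline sentence. On that reading nobody knows their arm at baseline. This is a fair possibility, and bias arises only if it is wrong for some participants. But the text does not settle it, and welcome messages sent on study entry point the other way if entry means enrollment or randomization.

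The illustration also depends on choices the plan has not made. Change scores, baseline adjustment and a 5% test are not named. A group effect averaged over all five surveys would be almost untouched. If only half the T2C arm shifted by d, the biases would halve. At d = 0.2 even the change-score bias is below its own standard error (0.20 against 0.258). These points stand and limit the size of the claim.

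A further point concerns the model. If knowing the arm shifted every survey equally by d, a baseline taken after disclosure would give biases of 0 (change score), (1 − r) × d (adjusted) and d (month 4 alone). With baseline taken first, all three would carry d. Reordering therefore does not cure a lasting reporting bias in an unblinded self-report trial. That is a different problem, and it does not justify measuring baseline after allocation may be known.

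Finally, this is a pilot and Aim 1 is unaffected. Both are true, but the pilot's comparison data are meant to guide the next trial.

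**Conclusion.** The concern holds as a conditional one. The written order puts the self-report baseline after randomization, and no safeguard appears in the text available. Estimates that use baseline are therefore exposed if participants can learn their arm, or start the intervention, before answering.

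Under an assumed 0.2 SD shift and correlation 0.6, the bias is 0.12 to 0.20 SD for the baseline-adjusted, group-by-time and change-score analyses. It is 0.04 SD in the opposite direction for an average over all surveys, and nil for follow-up alone. Neither the shift nor the correlation comes from the documents, and the direction is unknown. The point should be fixed because the remedy is cheap and a compromised baseline cannot be recovered; it does not invalidate the pilot. Confidence is medium, since actual practice may already be baseline first.

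**What to change.** Reorder the sequence in Study Objectives: consenting participants submit the online baseline battery, are then randomized and told their arm, and repeat the battery monthly through month 4. Release the PE link, or the T2C keyword prompt and welcome messages described in Study Design & Method, only once the baseline survey is recorded as submitted. If randomization has to come first, state that allocation is not disclosed and no intervention message is sent until then. State in Statistical Considerations how baseline enters the mixed models, so that the reader knows which estimates depend on it.

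The cost is a wording change and one ordering rule in the online workflow, with no extra visit or measure. People who consent but never submit baseline would not be randomized and should be reported as such. If 10% do not submit (an assumption), randomizing 50 needs 50/0.90, about 56 consents. At 5% it is 50/0.95, about 53, and at 20% it is 50/0.80, about 63.
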